9 STATISTICAL CONSIDERATIONS

9.1 STATISTICAL HYPOTHESES

- Primary Endpoint(s):
 - 1) The number of SPIRIT dyads who are congruent on goals of care at 2 weeks post-intervention will be significantly higher than that of control dyads.
 - 2) Patient decisional conflict scores at 2 weeks post-intervention will be significantly lower than those of control dyads.
 - 3) Surrogate decision making confidence (DMC) scores at 2 weeks post-intervention will be significantly higher than those of control dyads.

- 4) The number of SPIRIT dyads who are congruent on goals of care and confident surrogate (DMC=3 or higher) at 2 weeks post-intervention will be significantly higher than that of control dyads.
- Secondary Endpoint(s):
 - 1) HAD-anxiety scores in SPIRIT surrogates will be significantly lower than those of control surrogates at 3 months after the patient's death.
 - 2) HAD-depression scores in SPIRIT surrogates will be significantly lower than those of control surrogates at 3 months after the patient's death.
 - 3) PTSS-10 scores in SPIRIT surrogates will be significantly lower than those of control surrogates at 3 months after the patient's death.
- Exploratory: Among patients who have died,
 - 1) The percentage of patients hospitalized during the final month of life in the SPIRIT group will be significantly lower than that in the control group.
 - 2) The percentage of patients admitted to an ICU during the final month of life in the SPIRIT group will be significantly lower than that in the control group.
 - 3) The percentage of patients having intensive procedures during the final month of life in the SPIRIT group will be significantly lower than that in the control group.
 - 4) The length of hospital stay during the final month of life in the SPIRIT group will be significantly shorter than that in the control group.

For Supplement Aims:

- Aim 1:
 - 1) The number of SPIRIT dyads who are congruent on goals of care at 2-3 days post-intervention will be higher than that of control dyads.
 - 2) Patient decisional conflict scores at 2-3 days post-intervention will be lower than those of control dyads.
 - 3) Surrogate decision-making confidence (DMC) scores at 2-3 days post-intervention will be higher than those of control dyads.
 - 4) The number of SPIRIT dyads who are congruent on goals of care and confident surrogate (DMC=3 or higher) at 2-3 days post-intervention will be significantly higher than that of control dyads.

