9.2 SAMPLE SIZE DETERMINATION

We have an adequate sample size to detect clinically meaningful differences between SPIRIT and usual care for our primary outcomes. Statistical power is based on a random effects models: a generalized linear mixed model for binary outcomes (e.g., dyad congruence) and a linear mixed model for continuous outcomes (e.g., patient decisional conflict).

We conducted a simulation study to estimate power with 2-sided significance level alpha=.05, corrected for anticipated dropout and potential intraclass correlations (ICCs) ranging .01-.04, based on ICCs observed in our prior work. To estimate the power more conservatively, we used the effect sizes observed at 2 months²⁰ rather than those at 2 weeks,¹⁸ which are larger (e.g., for the composite outcome, *OR*=1.8 at 2 months, *OR*=4.4 at 2 weeks). The overall power to detect clinically meaningful differences is excellent for the primary outcomes and good for the post-death outcomes.

Power for comparing SPIRIT and usual care with 19 clusters				
Aim 1	Percent or min. difference	OR or variance	ICC ^a	Estimated power
Dyad congruence	48%	OR =2.0	0.02 0.04	0.92 0.84
Patient DCS	d =0.24	0.23	0.01 0.10	0.98 0.81
Surrogate DMC	d =0.22	0.20	0.01 0.10	0.99 0.80
Composite outcome	47%	OR =2.0	0.02	0.93
Aim 3				
Anxiety	d =1.35	7.0	0.01 0.03	0.84 0.80
Depression	d =1.60	10.0	0.01 0.03	0.85 0.79
PTSS-10	d =4.75	90.0	0.01 0.03	0.85 0.78

^a observed ICCs in our prior work; *d*=1/2 *SD*.

DCS, decisional conflict scale; DMC, decision-making confidence.

For Supplement Aims:

Because this is a pilot study, prior estimates of effect sizes were not available; thus a traditional sample size calculation was not performed. Instead we focused on calculating the minimum effect size that can be detected with adequate power (>=80%). Based on preliminary calculations, we found that a sample size of 30 will achieve 80% power to detect an effect size (Cohen's *f*²) of 0.28 (moderate-high), attributable to the treatment group indicator using an F-test at a 5% significance level. We will use the estimates of effect sizes obtained from this study for sample size calculations in future larger studies.

Supplement cohort study:

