9.3 POPULATIONS FOR ANALYSES

Patient-surrogate dyads will be the primary unit of analysis; all analyses will be intent to treat with all available data from all participants.

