9.4.2 ANALYSIS OF THE PRIMARY ENDPOINT(S)

SPIRIT effectiveness on the preparedness outcomes: Dyad congruence and the composite outcome (binary variables) will be analyzed by fitting a generalized mixed effects model for each, where the binary outcome is modeled in terms of a logit link⁹⁰ with both a random intercept and random slope to control for variation within and between subjects and clusters. The model also includes the intervention SPIRIT, cluster size and their interaction. For patient DCS and surrogate DMC scores, we will replace the logit link by the identity link with an additional error term. These models will allow us to examine whether SPIRIT was superior to usual care in the primary outcomes at 2 weeks and whether the effect of SPIRIT varies by cluster size. The analysis will be adjusted for potential covariates, such as race/ethnicity, and rural-urban status, in the model, including interaction between treatment and race/ethnicity.

For Supplement Aims:

To account for small sample size, resampling methods will be used for all analyses and 95% bootstrap confidence intervals of the differences in outcome scores will be reported.

- 1) Aim 1. SPIRIT effects on the preparedness outcomes:** For testing the effect of the intervention on dyad congruence, a paired binary outcome (congruent or not congruent), McNemar's test will be used. In addition, a logistic regression model will be used to test for differences in post-intervention outcomes by groups after adjusting for potential covariates. The adjusted ratio of odds of congruence in the intervention group versus the control group will be evaluated and reported as an effect size estimate.
- 2) Aim 1. SPIRIT effects on care decisions:** Differences in proportion of decisions made (e.g. stopping dialysis, DNR order, and hospice enrollment etc.) at 6-month follow up or death of patient will be described across groups and used as effect size. We will also explore time to event analysis to assess the difference in rate of risks between the two groups using non-parametric and semiparametric methods.
- 3) Aim 2. Surrogate post-bereavement distress (HADS scores):** Differences in the HADS subscale scores between the intervention and control groups will be assed using t-tests. Because, we estimate a 50% rate of death during the study, the number for this analysis would be n=15. A standardized difference between groups will be used as an effect size estimate.

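### Section 9.4.2 puts treatment interactions in the superiority model without saying which contrast is the overall SPIRIT effect, and does not name the collected baseline score as a covariate

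*Combined protocol and SAP*

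**What the plan says.** **The effect intended.** Section 9.1 states one arm comparison per primary outcome, for example "Patient decisional conflict scores at 2 weeks post-intervention will be significantly lower than those of control dyads". Section 9.3 says that "all analyses will be intent to treat with all available data from all participants". The table in 9.2 is headed "Power for comparing SPIRIT and usual care with 19 clusters" and mentions no interaction.

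**The model.** Section 9.4.2 fits a mixed model "with both a random intercept and random slope to control for variation within and between subjects and clusters" and adds that "The model also includes the intervention SPIRIT, cluster size and their interaction". The stated purpose is twofold, namely to learn "whether SPIRIT was superior to usual care in the primary outcomes at 2 weeks and whether the effect of SPIRIT varies by cluster size". Covariate adjustment follows, with race/ethnicity and rural-urban status as examples, "including interaction between treatment and race/ethnicity". The section does not say whether cluster size is the three-level stratum of 6.3 or a continuous census. It gives no coding, centring or averaged contrast, and no separate main-effect model. Section 9.4.7 then describes adding race and its interaction to the model as an extra step, so it is unclear whether the primary model already holds them.

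**The baseline value.** Section 8.1 has each preparedness outcome measured at baseline and again two weeks after Session II. Neither 9.4.2 nor the list of potential covariates in 8.1 names the baseline score. Section 6.3 provides for examining group imbalances and adjusting for them. Sections 9.4.3 and 9.4.9 reuse the 9.4.2 approach.

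**The concern.** Once a treatment interaction is in a model, the treatment coefficient is the effect where the other factor is at its reference or zero level. It equals the overall effect only if the terms are centred or if an average is taken explicitly. Two analysts following 9.4.2 could therefore report different quantities as the SPIRIT effect, with very different standard errors, for all four primary hypotheses.

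The baseline question is separate and smaller. An open covariate list, with adjustment tied to imbalances found later, lets the choice be made after the data are seen. It may also give up precision from data already in hand. Clinics are randomised before dyads are recruited (10.1.1.2) and clusters are few, so arms may differ at baseline.

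**Working it through.** **Inputs.** From 9.2: two-sided alpha 0.05; 19 clusters; patient decisional conflict (DCS) difference 0.24, variance v = 0.23; surrogate confidence (DMC) difference 0.22, variance 0.20. The table gives ICC 0.01 and 0.10 for these scores; 0.04 is the top of the range in the text. From 5.5: 400 dyads, so 400/19 = 21 per cluster and 19 x 21 = 399. Assumed: equal cluster sizes, balanced arms, the same true effect everywhere.

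**1. The plan's own power, as one overall contrast.** SE = sqrt[4v(1 + 20 ICC)/399]; power = Phi(difference/SE - 1.96).

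| | ICC | SE | Power | Stated |
|---|---|---|---|---|
| DCS | 0.01 | 0.0526 | 0.995 | 0.98 |
| DCS | 0.04 | 0.0644 | 0.96 | - |
| DCS | 0.10 | 0.0832 | 0.82 | 0.81 |
| DMC | 0.01 | 0.0490 | 0.994 | 0.99 |
| DMC | 0.10 | 0.0776 | 0.81 | 0.80 |

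The continuous-outcome powers match an overall effect, with no interaction and no baseline covariate, to within 0.02. Simple formulas do not reproduce the dyad congruence powers: they give 0.81-0.83 and 0.71-0.73 against 0.92 and 0.84. Those came from a simulation with unstated settings, and nothing below rests on them.

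**2. The reference-coded coefficient.** Assume strata of 6, 7 and 6 clusters, a six-cluster reference stratum (6 x 21 = 126 dyads) and race 50/50.

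- Size interaction only: variance = 4v(1 + 20 ICC)/126.
- Both interactions: add 0.5² x 16w/399 = 4w/399, where w = (1 - ICC)v.

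DCS at ICC 0.04: 0.92 x 1.8/126 = 0.01314, SE 0.115. Adding 4 x 0.2208/399 = 0.00221 gives 0.01536, SE 0.124.

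| ICC | Overall | Size only | Both |
|---|---|---|---|
| 0.01 | 0.995 | 0.73 | 0.63 |
| 0.04 | 0.96 | 0.55 | 0.49 |
| 0.10 | 0.82 | 0.37 | 0.34 |

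Generalised least squares over simulated allocations with near-equal strata gives 0.78, 0.61 and 0.41 (size only) and 0.67, 0.53 and 0.38 (both). DMC is about 0.01 to 0.02 lower. At ICC 0.04, with 4 or 9 of the 19 clusters in the reference stratum, DCS power with both interactions is 0.37 or 0.62. With the 28 clusters that the state counts in 6.3 add up to (14 dyads each), the three powers are 0.98, 0.67 and 0.58.

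**3. The averaged contrast.** With both interactions kept and the effect averaged over the sample, the DCS standard error at ICC 0.04 is 0.0647, the same as without interactions, and power is 0.96.

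**4. The target, if effects vary.** Suppose each non-reference size and race level has an effect larger by 0.10. An overall 0.24 then corresponds to a reference-cell coefficient of 0.24 - (2/3)(0.10) - (1/2)(0.10) = 0.12.

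**5. Baseline adjustment.** Variance = 4[b(1 - rc²) + w(1 - r²)/21]/19, where b = ICC x v, r is the baseline to follow-up correlation within clusters, and rc the same between clusters. The documents give no correlation, so r = 0.3-0.7 is assumed, with rc = 0 or rc = r.

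| ICC | Variance cut, rc = 0 | Variance cut, rc = r | DCS power |
|---|---|---|---|
| 0.04 | 5-26% | 9-49% | from 0.96 upward |
| 0.10 | 3-15% | 9-49% | 0.82 to 0.83-0.88, or 0.86-0.98 |

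**The case against.** The strongest reply is that the power loss is hypothetical. Section 9.4.2 never says the test is a reference-coded coefficient. It poses superiority and effect variation as two questions, and 9.1 defines the first as an overall comparison. That stands. A reader might infer that the trial tests SPIRIT in one size stratum only, or is underpowered for its primary outcomes. The documents support neither reading, because every low figure needs a coding choice that the plan does not make, together with assumed strata and race shares.

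A reader might also infer that the power inputs were baseline-adjusted, so that an unadjusted analysis contradicts them. Section 9.2 does say that "we used the effect sizes observed at 2 months", and section 2.2 reports that trial's effects adjusted for baseline. But the table's footnote sets the differences at half a standard deviation: sqrt(0.23)/2 = 0.24 and sqrt(0.20)/2 = 0.22. Section 2.2 gives adjusted coefficients of 0.13 for confidence and -0.19 (at 12 months) for conflict. The table does not show baseline-adjusted inputs.

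Nor does omitting baseline change what is estimated for DCS and DMC: with an identity link under randomisation it costs precision only. Finally, a random slope and within-subject variation may mean that baseline enters as a repeated response. That is possible, but no time or arm-by-time term is named, so that reading also lacks a stated primary contrast.

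**Conclusion.** The point holds as a gap in specification that should be fixed. The plan intends an overall arm effect and powers one, but 9.4.2 does not say which contrast delivers it, and 9.4.2 and 9.4.7 do not agree clearly on where the race interaction belongs. Centred coding or a marginal contrast costs nothing. The reference-coded coefficient would have DCS power of about 0.6, 0.5 and 0.3-0.4 at ICC 0.01, 0.04 and 0.10, given equal or near-equal size strata, race 50/50 and no true interaction.

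The missing baseline covariate is a forgone gain in precision for the two continuous scores: 5-49% of the arm-effect variance at ICC 0.04 and 3-49% at ICC 0.10, under assumed correlations of 0.3-0.7. The wording of the gap is certain. The magnitudes rest on the stated assumptions, and none is given for the two binary outcomes.

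**What to change.** In 9.4.2, make the primary test the overall arm effect at 2 weeks, adjusted for the baseline value of the same outcome, the randomisation size stratum and the covariates already named (race/ethnicity and rural-urban status), with a random intercept for cluster. Then do one of two things:

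- leave treatment interactions out of this model and test them in 9.4.7; or
- keep them and pre-specify a contrast averaged over the observed size and race distribution.

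Reconcile 9.4.2 with 9.4.7 on race. State that the same contrast applies in 9.4.3, with baseline HADS and PTSS-10 scores as covariates (both are collected under 8.1), and in 9.4.9, where the outcomes have no baseline value.

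If the random slope is meant to describe a repeated-measures model, name the time and arm-by-time terms and make the 2-week arm difference the primary contrast. Do not require equal baseline means across arms, because recruitment follows clinic allocation.

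The cost is wording only, since every variable is already collected. There are two downsides. For dyad congruence and the composite, the odds ratio becomes conditional on baseline. And baseline is measured after clinic allocation, so knowledge of the arm could affect it slightly.

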6.3 MEASURES TO MINIMIZE BIAS: RANDOMIZATION AND BLINDING

Clinics covered by the same care provider who will deliver SPIRIT sessions will be combined to one cluster to avoid risk of contamination; this results in clusters (4 in GA, 3 in NC, 8 in NM, 5 in PA and 8 in VA). Because the numbers of available patients substantially vary across the clusters, to minimize group imbalance clusters will be stratified to three sizes: small (patient census ≤ 52), medium (53-105), and large (≥ 106). We will randomize clusters to either SPIRIT or usual care plus delayed SPIRIT, with randomly permuted blocks (sizes of 2 and 4) within cluster size stratum nested in each state, using a pseudo-random-number generator, by the Study Coordination Center.

Before the study starts, the Study Coordination Center will inform the group assignment for each cluster to the site PIs, with a unique ID consisting of abbreviations for state and cluster size stratum. While the heterogeneity in minority race/ethnicity across clusters improves the study's generalizability, stratification or pairing clusters by race/ethnicity is not feasible because some clinics uniquely serve one race with no comparable clinics within state. Group imbalances on race/ethnicity and other potential confounding factors will be examined and adjusted for in the analyses. The cluster randomized design prevents blinding patient-surrogate dyads and dialysis care providers to group allocation. However, research staff assessing effectiveness outcomes will be blind to group assignment.

For Supplement Aims:

[name] (biostatistician/Co-I) will generate a randomization scheme using stratified (by race), permuted block randomization with block size 5, using a random-number generator. Dyads will be randomized with equal allocation (1:1) to SPIRIT or usual care. Due to the nature of the intervention, blinding dyads to their group allocation is impossible, but the research staff assessing outcomes will be blind. Immediately after the completion of the baseline assessment by phone, the data collector will open a sealed envelope to identify group assignment and schedule an intervention session to take place ~ 2 weeks hence for SPIRIT as well as a follow-up data collection session in the next 2-3 days.

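### In the dementia pilot, bootstrap intervals are offered as the small-sample safeguard, but the usual forms cover less than the ordinary t interval: slightly at 15 per arm, clearly at 7-8 bereaved surrogates per arm

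*Combined protocol and SAP*

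**What the plan says.** The statement opens the supplement part of Section 9.4.2: "To account for small sample size, resampling methods will be used for all analyses and 95% bootstrap confidence intervals". The same sentence goes on to give the scope of the intervals: "95% bootstrap confidence intervals of the differences in outcome scores will be reported". It does not say which bootstrap interval is meant, how many resamples are drawn, or whether resampling is within arm.

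The group sizes follow from three places. Section 9.2 sets the pilot at 30 dyads. Section 6.3 says "Dyads will be randomized with equal allocation (1:1) to SPIRIT or usual care", and 9.4.2 (Supplement Aim 3) confirms 15 in the SPIRIT arm. For post-bereavement HADS (Supplement Aim 2), 9.4.2 assumes 50% deaths, so that "the number for this analysis would be n=15". That is both arms together, or about 7-8 per arm.

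The same section plans t-tests for HADS with a standardized difference as effect size, and an adjusted odds ratio for congruence. For care decisions it plans a descriptive comparison ("Differences in proportion of decisions made"). Section 9.2 says the pilot's effect-size estimates will be used to size later studies.

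**The concern.** The plan names small numbers as the reason for using the bootstrap. The common bootstrap intervals have the opposite property. They resample from the observed data, so the variance they see is too small by the factor (n-1)/n, and they apply no t multiplier for the estimated variance. For a raw mean difference the result is shorter than the textbook t interval and misses the true value more often than 5% of the time.

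The pilot exists to estimate effects, so the interval is its main statement of uncertainty. The bereaved comparison is the most exposed. It is the smallest, and it has two planned methods, a t-test and a bootstrap interval, that can give different answers on the same contrast.

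**Working it through.** **Inputs from the documents.** 15 per arm (9.2, 6.3, 9.4.2); 15 bereaved surrogates in total, taken as 8 vs 7 (9.4.2); HADS subscales 0-21 and the confidence scale 0-4 (measurement tables, Section 3). **Assumptions.** Score shapes: normal, skewed HADS-like on 0-21, ceiling-type on 0-4. Care-decision rates are also assumed, since none is given.

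**The plan's own figure.** Section 9.2 states that "a sample size of 30 will achieve 80% power to detect an effect size" (Cohen's f-squared) of 0.28, "attributable to the treatment group indicator using an F-test at a 5% significance level". With a noncentral F on 1 and 28 df and noncentrality 0.28 × 30 = 8.4, power is 0.799. The stated 80% reproduces. The documents give no coverage figure for the bootstrap intervals.

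**Analytic check, raw mean difference, n per arm.**
- Half-width of the simple bootstrap relative to the t interval: 1.96 × sqrt((n-1)/n) / t(0.975, 2n-2).
- n = 15: 1.96 × sqrt(14/15) / 2.048 = 0.925. Approximate coverage 93.1%.
- n = 7.5 (the average of 8 and 7): 1.96 × sqrt(6.5/7.5) / 2.160 = 0.845. Approximate coverage 90.9%.

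**Simulated coverage of nominal 95% intervals, raw mean difference** (3,000-5,000 trials, 1,000 resamples within arm, simulation error about 0.5 point):

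| Interval | 15 vs 15 | 8 vs 7 |
|---|---|---|
| Percentile, basic | 92-94% (90-94% with ceiling-type scores) | 90-92% |
| BCa | 92-94% (90-94% with ceiling-type scores) | 87-90% |
| Studentised bootstrap | 95% (93% with ceiling-type scores) | 94-96% |
| t | 95% | 94-97% |

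The simple forms are about 8% narrower than t at 15 vs 15. At 8 vs 7 the percentile interval is about 16% narrower (mean widths 1.83 and 2.19 SD for normal scores; 1.83/2.19 = 0.84).

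**Disagreement with the planned t-test.** With 8 vs 7, normal scores and no true difference, the percentile interval covers zero in 89.7% of trials and the t interval in 94.1%. The bootstrap interval therefore excludes zero in 10.3% and the t-test rejects in 5.9%. The two must disagree in at least 10.3 - 5.9 = 4.4% of trials.

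**Smaller bereaved groups.** If each patient dies with probability 0.5, an arm of 15 has 5 or fewer deaths with probability 0.151. At least one arm does so with probability 1 - (1 - 0.151)² = 0.28. At 5 vs 5 the simple bootstrap covers 87-90%.

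**Standardized difference (the stated Aim 2 effect size), normal scores.** Percentile: 91-94% at 15 vs 15 and 88-90% at 8 vs 7. Basic: 97-99%. At 8 vs 7 with no true difference the mean width is 2.39, against 2.19 for the t interval in SD units.

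**Difference in proportions, 15 per arm, percentile interval, exact enumeration at assumed rates.**
- Rates of about 0.3 to 0.65: 93-96%.
- 0.20 vs 0.10: 90%. 0.15 vs 0.05: 87%.
- 0.10 vs 0.10: 98%. 0.05 vs 0.05: 99.5%.
- Newcombe score interval: 94-99.9% throughout.

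**The case against.** Several points on the other side stand.

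- **The type is not named.** A studentised bootstrap is permitted by the present wording and is close to nominal for scores. Under-coverage therefore depends on a choice the plan has not stated. But the plan does not require the form that works, and the common forms lack the property for which the bootstrap is invoked.
- **A reader might infer that intervals at 15 per arm fall well below 95%.** For scores they do not. The shortfall is mostly 1-3 points, up to 5 with ceiling-type scores.
- **A reader might infer that care decisions are rare and that their intervals would fail badly.** The documents support neither step. They give no rate; Section 2.1 describes such decisions as near at hand for these patients, and 4.1 expects about half the sample to die within 12 months. The interval clause names outcome scores only. A bootstrap interval for a proportion follows only from the words about all analyses, and it performs adequately at moderate rates.
- **A reader might infer that every bootstrap interval here is too short.** The one for the standardized difference is wider than the t interval in SD units, although its percentile form still under-covers.
- **HADS already has t-tests.** True, but this makes the two methods inconsistent and does not remove the bootstrap interval.
- **The stakes are modest.** Section 9.2 carries forward effect-size estimates, and the choice of interval does not change a point estimate. This is a 30-dyad pilot supplement.

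**Conclusion.** The point holds in limited form. For raw mean differences, the usual bootstrap intervals do not do what 9.4.2 uses them for. The loss is small at 15 per arm (about 92-94%, as low as 90% with ceiling-type scores). It is clear at 7-8 bereaved surrogates per arm (about 90%, range 87-92%), where the miss rate is roughly double the nominal 5%. For proportions, the effect is conditional on reading the resampling statement to include them and on low, unequal rates; when both rates are low and equal, the percentile interval over-covers.

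The figures rest on the assumed score distributions and event rates, on resampling within arm, and on the expected 50% mortality. If a studentised bootstrap was intended for scores, the remaining defect is that the plan does not say so. The parent trial's primary and secondary analyses are not touched.

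**What to change.** Replace the sentence in 9.4.2 with named intervals:

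- **Decisional conflict, surrogate confidence and HADS differences:** t-based 95% intervals. If resampling is preferred, use a studentised bootstrap, resampled within arm, with the number of resamples stated.
- **Standardized HADS difference:** a noncentral-t interval.
- **Any difference in proportions, including care decisions:** a Newcombe score interval.
- **Congruence:** keep the planned adjusted odds ratio.

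With t-based intervals for HADS, the test and the interval agree if both use the same variance form. The cost is one passage of SAP wording and somewhat wider intervals: relative to the percentile form, about 1/0.925 = 1.08 times as wide at 15 per arm and about 1/0.84 = 1.19 times at 8 vs 7. No data collection or sample size changes.

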4 STUDY DESIGN**4.1 OVERALL DESIGN**

We will conduct a dialysis clinic-level cluster randomized trial with two groups, SPIRIT versus usual care followed by delayed SPIRIT. We will recruit 400 dyads of patients on chronic (“prevalent”) dialysis who are at high risk of death in the next year and their surrogate decision-makers (total 800 individuals) from 30 free-standing dialysis clinics in 4 states. The primary outcomes are patient and surrogate self-report preparedness for end-of-life decision making. The implementation evaluation data will be obtained throughout the study course. Upon patient death (anticipate 20% of patients; n = ~ 80), we will assess surrogates’ post-bereavement distress. Patient participation will end at 9 months (to allow for obtaining Medicare claims data during the study period) or death, whichever occurs first; surrogate participation will end at 9 months or at the completion of 3-month post-death follow-up. If patient is still living at 9 months, we will ask for an extension of follow up period to include 12 more months. Medicare claims data for end-of-life treatment intensity will be obtained quarterly. Clinics assigned to usual care will receive the delayed implementation, SPIRIT, in Year 4, Q1. This is a Phase III trial of an intervention that involves minimal risks and has proven to be efficacious, and thus no interim analysis is planned.

For Supplement Aims:

We will use a randomized controlled trial design with two groups: SPIRIT-dementia and usual care. From the pool of screened but excluded ESRD patients, we will recruit 30 dyads of patients with mild to moderate dementia and their surrogates. The groups will be stratified by race (white vs non-white). Patient and surrogate self-reported preparedness for end-of-life decision making will be measured at baseline and shortly after the intervention (by phone in the next 2-3 days) as done in the pilot test of SPIRIT-dementia. Additionally, we will review the patient's medical record to examine care decisions at 6 months or after the patient's death, whichever occurs first. In the case of patient death, we will also assess surrogates' post-bereavement outcomes (anxiety and depression symptoms) at 1 month after the patient's death. Based on previous research,¹³ we anticipate about 50% of the supplement sample will die within 12 months of enrollment. All data collection from study participants will be telephone-based.

Supplement cohort study:

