- **The preparedness outcomes measures** will be assessed at baseline and 2-3 days after the intervention.
- **Surrogates' post-bereavement psychological distress** will be assessed using the HADS, which will be completed at baseline and 1 month post patient death.
- **Patients' level of articulation of end-of-life wishes:** Using a "quantitizing" technique of qualitative data analysis,³⁹ two raters will independently review SPIRIT session transcripts focusing on the values of

treatment outcomes and the goals of care discussions and rate the level of patient's articulation of end-of-life care preferences on a 3-point scale (3=expressed wishes very coherently, 2=somewhat coherently, 1=unable to express wishes coherently). Inter-rater reliability (percent agreement) will be established, targeting $\geq 90\%$.

- **Care decisions (assessed at 6 months post intervention or after the patient's death, whichever occurs first):** Stopping dialysis, DNR order, and hospice enrollment are major care decisions that must involve the treating physician (or APRN) and social worker. These decisions are also required to be documented in the CMS Form 2746 in the event of a dialysis patient's death. On a monthly basis, the research coordinator will check in with the outpatient dialysis APRN to track these care decisions and will be aggregated at 6 months.
- **Descriptors and Potential Covariates (collected at baseline):** Patients and surrogates will each complete a Sociodemographic Profile which includes demographic information and previous end-of-life decision-making experience. Patients' clinical characteristics (e.g., date of dementia diagnosis, etiology of dementia, and comorbid conditions) will be abstracted from the patient's medical records.

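### Dementia pilot: McNemar's test is named for the intervention effect on congruence but contains no arm comparison, and the plan does not say that the between-group logistic model decides the hypothesis

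*Combined protocol and SAP*

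**What the plan says.** The supplement is a two-arm trial. Section 4.1 states: "We will use a randomized controlled trial design with two groups: SPIRIT-dementia and usual care". Section 6.3 adds: "Dyads will be randomized with equal allocation (1:1) to SPIRIT or usual care". Randomisation is stratified by race, and dyads are not matched across arms.

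The first supplement hypothesis in section 9.1 is between-group: "The number of SPIRIT dyads who are congruent on goals of care at 2-3 days post-intervention will be higher than that of control dyads".

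Congruence is a single value per dyad. Under section 8.1 the preparedness measures "will be assessed at baseline and 2-3 days after the intervention".

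The supplement part of section 9.4.2 then gives two analyses of congruence. The first opens with its purpose, "For testing the effect of the intervention on dyad congruence", describes congruence as "a paired binary outcome (congruent or not congruent), McNemar's test will be used", and does not say what is paired or whether the test is run per arm or on both arms together. The second follows at once: "In addition, a logistic regression model will be used to test for differences in post-intervention outcomes by groups after adjusting for potential covariates". The effect size comes from this second model: "The adjusted ratio of odds of congruence in the intervention group versus the control group will be evaluated". The same section promises resampling methods and 95% bootstrap intervals. Nothing says which of the two tests settles the hypothesis.

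**The concern.** McNemar's test uses only the units whose two paired binary values differ, and asks whether changes in one direction outnumber changes in the other. It has no term for treatment arm. Applied to baseline and follow-up congruence in the SPIRIT arm, it ignores the control arm. Applied to all 30 dyads, it merges the arms. In both cases it answers whether congruence changed, while the hypothesis asks whether the arms differ.

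At stake is how the pilot's congruence result is labelled and read. Repeating the same tool, or the conversation that the study itself prompts at home, could move both arms in the same direction. McNemar's test would count that movement, and under the present wording its p-value would be reported as a test of the intervention's effect. With a second test of the same claim beside it and no rule for choosing, the two can disagree and either could be reported as the answer.

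**Working it through.** **1. What could be paired.**
- *SPIRIT dyad with control dyad:* not available, because the arms are unmatched (sections 4.1 and 6.3).
- *Patient answer with surrogate answer:* each scenario in section 8.1 has three response options, so the answers are not binary. If they were collapsed, McNemar's test would compare the two marginal proportions, which is neither congruence nor an arm comparison.
- *Baseline with follow-up congruence in the same dyad:* this fits the outcome and the assessment times, but it tests change over time.

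No available pairing tests the between-group hypothesis. This step needs no assumed rates.

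**2. The plan's own figure.** Section 9.2 states 80% power at N = 30, Cohen's f² = 0.28 and a 5% F-test on the treatment group indicator. The noncentrality is 0.28 × 30 = 8.4, with 1 and 28 degrees of freedom. Power is 0.799, so the figure reproduces. It belongs to an arm comparison and says nothing about McNemar's test.

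**3. How often McNemar's test rejects when the arms do not differ.** Let b dyads gain congruence and c lose it. The exact two-sided p-value is min{1, 2 × P[Bin(b + c, ½) ≤ min(b, c)]}. Its rejection rate is the sum of the multinomial probabilities of all (b, c) with p ≤ 0.05. At least six dyads must change: five in one direction give 2 × (½)⁵ = 0.0625, and six give 2 × (½)⁶ = 0.031.

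Inputs: n = 15 in the SPIRIT arm (section 9.4.2), or n = 30 if the arms are pooled. The documents give no congruence rates for this pilot, so the gain and loss rates, equal in both arms, are assumptions shown as a range. The last column is a 5% chi-square test between arms at 15 per arm, taking 40% congruent at baseline (also assumed) plus the net change.

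| Gain / loss (assumed) | Net change | McNemar, n = 15 | McNemar, n = 30 pooled | Between-arm chi-square |
|---|---|---|---|---|
| 10% / 5% | 5 points | 0.1% | 2% | 4.6% |
| 20% / 5% | 15 points | 4% | 24% | 4.6% |
| 30% / 5% | 25 points | 17% | 57% | 5.2% |
| 40% / 5% | 35 points | 38% | 82% | 5.4% |

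The McNemar columns follow the shared change. The between-arm column stays near 5%.

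**4. The opposite failure.** Suppose SPIRIT stays at 40% congruent, with 5% gaining and 5% losing, while control falls to 10% (assumed). McNemar's test in the SPIRIT arm rejects in about 0% of pilots. The between-arm chi-square rejects in 51%.

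**The case against.** The strongest reply is that the valid test is already in the plan. The sentence after the one on McNemar's test compares the groups, and its adjusted odds ratio is the reported effect size. This stands. A reader might infer that the pilot has no between-group test of congruence, and the documents do not support that.

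A reader might also infer that the McNemar result will drive future sample sizes. Section 9.2 does say that the pilot's effect sizes will be used for later studies, but for congruence that effect size is the between-group odds ratio. No McNemar output is designated for this purpose.

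Nor can McNemar's test be called the lead or primary test. It is listed first, but the plan does not rank the two analyses. The supplement aim is worded as estimation, its first hypothesis does not ask for significance, and bootstrap intervals are planned. In a 30-dyad pilot little turns on one p-value.

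On size, the large rejection rates need usual-care dyads to gain a net 25 to 35 points between baseline and follow-up. Going by section 6.3, that is about 14 days plus 2 to 3 days. Nothing in the documents supports so large a shift without an intervention. At n = 15 the rate is below 5% in the two smaller scenarios, and the n = 30 column assumes a pooling that the plan does not state.

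What survives is narrower: the test is assigned to a purpose that it cannot serve, and no rule says that the valid test governs.

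**Conclusion.** The point holds as an error of assignment. As written, section 9.4.2 gives McNemar's test the task of testing the intervention's effect on congruence, and no pairing in this design lets it do that. This conclusion rests on the design alone.

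The practical size is uncertain and depends on change shared by both arms. Over the assumed range, false indications of an effect run from 0.1% to 38% within the SPIRIT arm, and from 2% to 82% if the arms are pooled. These figures show how the test behaves; they do not forecast this pilot. The consequence is limited by the pilot's size and by the between-group effect estimate that the plan already specifies. The correction is still worth making, because it is cheap and stops shared change from being reported as an effect of SPIRIT.

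**What to change.** In the supplement part of section 9.4.2:
- State that the sole test of supplement hypothesis 1 is the logistic regression of post-intervention congruence on randomised group. Name the covariates as baseline congruence and the race stratum, as far as 30 dyads allow, and report the planned bootstrap interval with it.
- Relabel McNemar's test as a descriptive within-arm analysis of change from baseline to follow-up, run separately in each arm, and remove the wording that assigns it to the intervention's effect.

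The cost is an edit to the analysis text. The model, the baseline measurement and the bootstrap are already planned, so no new data, visits or participants are needed.
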